3.20 Justification for sample size and details of the power calculation

The sample size calculations are based on the primary outcome measure, 30 day mortality. There are no data available in the UK on 30 day mortality in critically ill patients receiving tracheostomies so we used hospital mortality as a surrogate for 30 day mortality. There are a number of estimates of hospital mortality in tracheostomised patients on which to base the calculations.

The survey of 35 UK ICUs gave a mean value of 21 per cent for ICU mortality for tracheostomised patients. Hospital mortality is invariably higher than ICU mortality³¹, the mean increase in mortality between ICU and hospital discharge in the UK is 9.3 per cent absolute. Thus the predicted hospital mortality for these tracheostomised patients would be slightly over 30 per cent. This is very close to the UK average hospital mortality for all ICU admissions of 30.8 per cent³¹.

A meta-analysis carried out in 2005 of four methodologically sound published trials of tracheostomy timing show a relative risk reduction of 21 per cent.

Figure 2: Forest plot showing random effects meta-analysis of relative risk (95% confidence interval) of mortality with early compared with late tracheostomy.

We therefore selected a 21 per cent relative reduction in mortality as the clinically significant difference we wished our trial to detect.

Using a difference in hospital mortality of 21 per cent relative, 6.3 per cent absolute, with a predicted mortality in the “late” arm of 30 per cent, with an 80 per cent certainty of detecting a real difference and an alpha value of 0.05 the calculated sample size with a continuity correction is 1616 patients (808 in each arm).

In a recently completed multicentre study of pulmonary artery catheters in ICU patients (PAC-Man), 2.4 per cent of recruited patients or their relatives subsequently withdrew their consent, or were randomised in error. A similar dropout rate in this study would require a total of 828 patients per arm (1656 total). In addition there will be a cross-over rate, again using PAC-Man data we estimate this to be 2 per cent in the late arm. This gives a required sample size of 846 patients per arm (1692 total). This value has been chosen as the sample size for the trial.

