We have reviewed the effects that differing estimates of hospital mortality might have on the power of the study. The absolute difference detectable at the same power is slightly higher (i.e. the trial would be less sensitive) if the true mortality in the late arm exceeds that predicted, but would be lower if the true late mortality is less than that predicted. Table 1 below summarises the effects of differing estimates of hospital mortality would have on the power of the study assuming the same sample size and levels of certainty.

A study size of 1692 patients will allow a difference of less than one day in the secondary outcomes of length of ICU and hospital stay to be detected. Data are not available to estimate the power to detect changes in antibiotic use and sedative use.

Table 1: Hospital mortality estimates

Source of estimate	Hospital mortality (%)	Relative mortality reduction detectable	Absolute mortality reduction detectable
Lowest value from survey of UK ICUs	9%	42.2%	3.8%
Highest value from survey of UK ICUs	58%	12.2%	7.1%
Literature review	38.1%	17.8%	6.8%
SICS audit	8%	43.8%	3.5%

Should the TracMan trial obtain further funding, it could be extended to both increase the certainty of detecting a 21 per cent relative reduction in mortality, and increase the chances of detecting a lesser treatment effect. Table 2 below gives the sample size required to detect a 21 per cent relative reduction in mortality from a control group mortality of 30 per cent for a power of 90 per cent, 95 per cent, and 99 per cent.

Table 2: Sample size calculations

Power	Total sample size with continuity correction	Sample size allowing for crossovers and dropouts
80%	1616	1692
90%	2140	2284
95%	2630	2806
99%	3690	3938

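### Table 2 of section 3.20 applies two different loss allowances under one heading: 4.7% at 80% power and 6.7% at 90%, 95% and 99%

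*Protocol*

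**What the plan says.** Protocol section 3.20 takes a late-arm mortality of 30% and sets the target effect as follows: "Using a difference in hospital mortality of 21 per cent relative, 6.3 per cent absolute". Power is 80%. The unadjusted requirement is then stated in these terms: "an alpha value of 0.05 the calculated sample size with a continuity correction is 1616 patients (808 in each arm").

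Two allowances are then added in turn. Dropout of 2.4%, taken from PAC-Man, raises 808 to 828 per arm (1656 in total). For crossover the section says "again using PAC-Man data we estimate this to be 2 per cent in the late arm", and this raises 828 to 846 per arm (1692 in total), the planned size in section 3.19. The formula for the crossover step is not given.

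Table 2 is introduced with "Should the TracMan trial obtain further funding, it could be extended". It keeps the same 21% relative effect and the same 30% late-arm rate, and its added rows are "for a power of 90 per cent, 95 per cent, and 99 per cent". Its last column, "Sample size allowing for crossovers and dropouts", reads 1692, 2284, 2806 and 3938 against unadjusted totals of 1616, 2140, 2630 and 3690. No other dropout or crossover rate is given for the added rows.

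**The concern.** The four rows are presented as differing only in power, so the step from the unadjusted to the adjusted total should be the same multiplier in each, apart from rounding. It is not. Three rows share one multiplier, and the 80% row, which sets the trial's size, has a smaller one.

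Two things are at stake. Table 2 is the protocol's basis for sizing a funded extension, and the step from 1692 to 2284 combines a gain in power with a change of allowance, so it is not a like-for-like cost of moving from 80% to 90%. In addition, if the larger multiplier is the intended one, the planned 1692 does not deliver the stated 80% power after losses.

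**Working it through.** **Inputs (section 3.20).** Late arm p1 = 0.30. Early arm p2 = 0.30 − 0.063 = 0.237. Alpha 0.05, taken as two-sided because the section does not say. Equal arms. Dropout 2.4%. Crossover 2%, late arm.

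**Step 1: reproduce the unadjusted column.** With d = p1 − p2 = 0.063 and p̄ = 0.2685, the uncorrected size per arm is

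n = [z(0.975)·√(2p̄(1−p̄)) + z(power)·√(p1(1−p1) + p2(1−p2))]² / d²

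and the continuity-corrected size is n_c = (n/4)·[1 + √(1 + 4/(n·d))]².

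| Power | n_c per arm | Rounded up | Total | Table 2 |
|---|---|---|---|---|
| 80% | 807.1 | 808 | 1616 | 1616 |
| 90% | 1069.4 | 1070 | 2140 | 2140 |
| 95% | 1314.7 | 1315 | 2630 | 2630 |
| 99% | 1845.0 | 1845 | 3690 | 3690 |

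All four match, which also supports the two-sided reading. Any inconsistency therefore lies in the loss allowance alone.

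**Step 2: the multipliers in Table 2.**

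- 80%: 1692/1616 = 1.0470
- 90%: 2284/2140 = 1.0673
- 95%: 2806/2630 = 1.0669
- 99%: 3938/3690 = 1.0672

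Multiplying each by 0.976 removes the dropout step and leaves 1.022 for the 80% row and 1.041 to 1.042 for the other three.

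**Step 3: try single rules on all four rows.** Each starts from 808, 1070, 1315 and 1845 per arm, rounds up per arm, and doubles.

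| Rule | 80% | 90% | 95% | 99% |
|---|---|---|---|---|
| Table 2 | 1692 | 2284 | 2806 | 3938 |
| Additive loss: n/(1 − 0.024 − 0.02) | **1692** | 2240 | 2752 | 3860 |
| Sequential loss: n/0.976/0.98 | 1690 | 2238 | 2750 | 3858 |
| Dropout, then squared crossover: n/0.976/0.98² | 1726 | **2284** | **2806** | **3938** |
| Dropout, then linear 4% crossover: n/0.976/0.96 | 1726 | **2284** | 2808 | 3940 |

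Bold marks an exact match. A fifth check put the dilution directly into the late-arm rate (0.30 − 0.02 × 0.063 = 0.29874), recomputed the size, and divided by 0.976. That gives about 1719, 2279, 2801 and 3930: close to the three extension rows and 27 above the 80% row.

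No rule tried gives all four rows. Rounding up per arm moves a total by about 2 patients. The gaps between the additive rule and Table 2 are 2284 − 2240 = 44, 2806 − 2752 = 54 and 3938 − 3860 = 78. The gap between the squared rule and the 80% row is 1726 − 1692 = 34. (Before rounding, the squared rule gives 862.004 per arm at 80% power, so rounding to nearest would give 1724 and a gap of 32.)

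**Step 4: power of 1692 under the squared rule.** Effective size per arm = 1692 × 0.976 × 0.98² / 2 = 793.0. Inverting the continuity correction gives an uncorrected n of 761.6, so z(power) = (√761.6 × 0.063 − 1.960 × 0.6267)/0.6252 = 0.816 and power is 79.3%. The same inversion at 808 per arm gives 80.05%.

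**The case against.** The strongest counter-argument is that the three extension rows may be right. Section 3.22 specifies an intention-to-treat comparison, so patients who cross over stay in the analysis and dilute the effect rather than disappear. The usual allowance for that is 1/(1 − c)². With the stated 2.4% and 2%, rounded up per arm, it gives exactly 2284, 2806 and 3938.

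This stands, and it rules out a stronger claim that a reader might infer from the multipliers: that the extension rows use about twice the stated crossover and so do not follow from section 3.20. A linear 4% and a squared 2% are almost the same number (1/0.96 = 1.0417; 1/0.98² = 1.0412), so the table cannot tell them apart, and the section gives no formula that excludes the squared form.

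Nor does the worked example settle the matter for the 80% row. In sequence, 828/0.98 = 844.9 and 828 × 1.02 = 844.6, both of which round to 845 and not to the stated 846. Only the additive form, rounded up, reaches 846, and the section does not describe that form.

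It is also fair to say that the size is small next to the other assumptions, which include hospital mortality standing in for 30-day mortality and a crossover rate borrowed from a catheter trial. This limits the weight of the point. It does not make the four rows consistent: the squared reading moves the anomaly to the 80% row.

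**Conclusion.** Table 2 mixes two loss allowances, 4.7% in the 80% row and 6.7% in the other three, although section 3.20 states a single set of rates. That follows from the table's own figures and does not depend on any choice of formula.

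Which rows are wrong cannot be established from the protocol. If crossover is an additive loss, the extension rows are too high by 44, 54 and 78 patients. If it is squared effect dilution, the extension rows are right and 1692 is 34 patients short by the same method, with about 79.3% power in place of 80%. On either reading the discrepancy is about 2% of the sample size and under one percentage point of power. The point is minor: it affects the sizing of a possible extension and the exactness of the stated power, and no analysis or decision rule.

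The figures assume a two-sided 0.05 test, the 30% and 23.7% mortality rates, and rounding up per arm.

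**What to change.** State in section 3.20 how the 2% crossover enters the calculation, and apply that rule to all four rows of Table 2:

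- **Additive loss:** 1692, 2240, 2752 and 3860. The three extension figures change.
- **Squared effect dilution:** 1726, 2284, 2806 and 3938. The extension figures stay. The planned 1692 can also stay, with its power after losses restated as about 79.3%.

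The three extension figures should not be overwritten until the sponsor confirms the intended formula. If the squared form was meant, that change would replace correct numbers and undersize an extension by about 2%.

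The cost is one sentence and a few table entries. No extra enrolment is needed on either reading.

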3.21 Planned recruitment rate

To ensure generalisability of the results we plan to recruit a minimum of 30 ICUs to take part in the study. From the results of the UK survey we expect these units will average 450 admissions/year with a predicted mean rate of tracheostomy of 16 per cent. With 30 ICUs this gives a potential pool of 2160 patients per year to recruit to the trial. If an estimated 30 per cent of these patients are unsuitable for recruitment to the trial, the pool of potential recruits decreases to 1512. Allowing for time to initiate and train each ICU, and time to collect the hospital mortality data at the end of the study, the recruitment phase of the study should take between 18 months and 2 years.

An alternative estimate has been derived from the North Thames ICU database of 53,135 ICU admissions. In this database 10.6 per cent of admissions remained in the ICU for 10 days or more. The long-stay patients had a tracheostomy rate of 42 per cent. Using the same estimates of unit numbers and ICU admissions above a potential pool of 601 patients per year would be available to recruit to the trial. Using the assumptions above this would give a trial duration of between 3 and 3¹/₂ years.

3.22 Type of analysis

The principal comparisons will be between those allocated to “early” tracheostomy and those allocated to “late” tracheostomy (the “intention to treat” principle). The primary outcome variable will be proportion of patients surviving to 30 days post randomisation in each arm which will be compared using Fisher’s exact test.

Hospital and ICU mortality will also be compared between arms using Fisher’s exact test. The survival curves for the two arms will be calculated using the Kaplan-Meier method, with the starting time being the time of randomisation, and compared using a log-rank test. Differences in length of ICU stay, hospital stay, number of days sedated and number of antibiotic-free days between arms will be tested using the Wilcoxon rank-sum test.

Mr [name], Senior Statistician at ICNARC, will act as trial statistician and perform the analyses.

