3.4 Outcome measures

Primary outcome measure: Mortality 30 days after randomisation.

Secondary outcome measures: Mortality rate at discharge from hospital
ICU length of stay
Hospital length of stay
Mortality rate at (first) discharge from ICU
Number of days receiving sedative medication
Number of antibiotic-free days.

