3.9 Formal trial entry and random allocation

Allocation to a treatment arm will be made randomly. A central specialist telephone randomisation service will be used.

Randomisation will occur once a patient meets the inclusion criteria and has consented to the trial. When a clinician contacts the randomisation service, basic descriptive information will be requested. Once these details have been supplied, the random allocation will be given in return. The allocation will be minimised according to the patient's age and sex, broad diagnostic category, and the recruiting ICU.

The nature of the intervention means that blinding of allocation is impossible.

A member of the TracMan team will be available 24-hours a day, 7 days a week, to address any emergency recruitment issues. The contact details for this person will be available from the randomisation service.

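### Allocation is minimised on four prognostic factors, but the primary mortality test is an unadjusted Fisher's exact test: valid and adequately powered, but conservative, giving up about 3 to 4 points of power

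*Protocol*

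**What the plan says.** - Section 3.9 (allocation): "The allocation will be minimised according to the patient's age and sex, broad diagnostic category, and the recruiting ICU".
- Section 3.4 (primary outcome): "Primary outcome measure: Mortality 30 days after randomisation".
- Section 3.22 (primary analysis): by intention to treat, the proportion "surviving to 30 days post randomisation in each arm which will be compared using Fisher’s exact test". The same test is used for mortality in hospital and in the ICU. The log-rank and Wilcoxon tests for the other outcomes are also given without strata or covariates.
- Section 3.23 lists subgroup and exploratory analyses only. None is an overall treatment comparison adjusted for the minimisation factors.
- Section 3.20 (sizing): a late-arm death rate of 30% and a target reduction of "21 per cent relative, 6.3 per cent absolute", for 80% power at a significance level of 5%. The stated result is: "the calculated sample size with a continuity correction is 1616 patients (808 in each arm").

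A separate analysis plan may exist and was not available. The protocol does not leave the primary test to it, however: section 3.22 names the test.

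**The concern.** Minimisation makes the arms more alike on prognostic factors than chance would. The difference in mortality between arms then varies less from trial to trial than simple randomisation implies. Fisher's exact test still refers the result to the simple-randomisation distribution, so it rejects too rarely. Fisher's test is also conservative in its own right because the data are discrete. The two effects add.

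At stake is efficiency on the primary question. The actual type I error lies below the nominal 5%, and power that the design has already paid for, by balancing on these factors, is not collected.

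**Working it through.** **1. Reproduce the plan's figure.** Inputs from section 3.20: p1 = 0.30, p2 = 0.30 × (1 − 0.21) = 0.237, difference d = 0.063, alpha 0.05 (two-sided, which is what reproduces the figure), power 80%.

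- Without continuity correction, with p̄ = 0.2685: n = [1.960 × √(2 × 0.2685 × 0.7315) + 0.842 × √(0.30 × 0.70 + 0.237 × 0.763)]² / 0.063² = 776 per arm.
- With correction: n' = (n/4) × [1 + √(1 + 4/(n × d))]² = 194 × [1 + √(1 + 4/48.9)]² ≈ 807.4, rounded up to 808 per arm, 1616 in total. This matches the protocol. The same formula gives 2140, 2630 and 3690 for the other rows of Table 2.

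**2. Fisher's test under simple randomisation (exact enumeration).** Power is 80.1% at 808 per arm and 82.0% at 846 per arm (no dropout or crossover). Actual size at nominal 5% is about 4.4%. The sizing and the named test therefore agree with each other.

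**3. Prognostic strength of the factors.** The protocol gives none directly. The only internal guide is Appendix 4. A random-intercept logistic fit to the 21 units that report both tracheostomy numbers and ICU mortality gives a between-ICU SD of 0.43 on the logit scale. The 58.2% unit has only 12 tracheostomies (about 7 deaths); without it the SD is 0.38. The effects of age and diagnosis are assumptions. A combined SD of 0.45 represents roughly the ICU effect alone. Adding an assumed age effect of 0.6 log-odds per SD gives √(0.45² + 0.60²) = 0.75.

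**4. Simulation with allocation balanced within 20 prognostic strata, 800 per arm, overall mortality 30% vs 23.7%.**

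| Combined logit SD | Quantity | Fisher | Unadjusted Pearson | Stratified |
|---|---|---|---|---|
| 0.45 | Power | 80.0% | 81.7% | 82.9% |
| 0.45 | Size | 3.8% | 4.4% | 4.7% |
| 0.75 | Power | 81.0% | 82.4% | 84.7% |
| 0.75 | Size | 3.5% | 4.0% | 5.1% |

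Splitting the power difference:
- SD 0.45: total 82.9 − 80.0 = 2.9 points, of which 1.7 is Fisher to Pearson (discreteness) and 1.2 is Pearson to stratified (the factors).
- SD 0.75: total 84.7 − 81.0 = 3.7 points, of which 1.4 is discreteness and 2.3 is the factors.

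**5. Wider range, using adjusted logistic regression, 808 per arm, 8000 runs per setting.**

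| Combined logit SD | Power, Fisher | Power, adjusted | Gain (points) | Size, Fisher | Size, adjusted |
|---|---|---|---|---|---|
| 0.3 | 80.6% | 82.0% | 1.4 | 4.6% | 5.2% |
| 0.5 | 80.7% | 82.8% | 2.1 | 4.1% | 5.2% |
| 0.8 | 81.7% | 85.5% | 3.8 | 3.6% | 5.2% |
| 1.2 | 83.8% | 89.2% | 5.4 | 2.9% | 5.2% |

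The Monte Carlo standard error of one power figure here is √(0.8 × 0.2 / 8000) ≈ 0.45 points. The two simulations agree in direction and at the upper end; at the lower end they scatter between about 2 and 3 points.

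**6. In patients.** By the normal approximation, moving from 80% to 83% or 84% power by sample size alone multiplies N by (1.960 + 0.954)² / (1.960 + 0.842)² = 1.08, or (1.960 + 0.994)² / (1.960 + 0.842)² = 1.11. That is 8 to 11% of 1616, about 130 to 180 patients.

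**The case against.** The case for leaving section 3.22 alone is substantial, and most of it stands.

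- The plan is coherent: the continuity-corrected sizing matches a Fisher test, and the stated 80% power is met. A reader might infer that the trial is under-powered; the figures do not support that.
- The error is in the safe direction. A reader might infer that ignoring the minimisation factors invalidates the test or inflates false positives; it does the opposite.
- It is tempting to attribute the whole loss to ignoring the factors. About 1.5 points come from Fisher's discreteness and would be recovered by an ordinary unadjusted chi-squared test.
- The survey range of 9% to 58% in Table 1 might be read as proof of large differences between ICUs. The top figure rests on one unit with 12 tracheostomies, the next highest is 33.2%, and these are ICU deaths in patients already tracheostomised, not 30-day deaths in randomised patients.
- A reader might count the absence of a stated effect estimate or confidence interval as an error. That is detail commonly left to an analysis plan, and is not counted here.
- Minimisation over four margins is likely to balance each factor less tightly than the simulated strata, so Fisher's actual size may be nearer the 4.4% of simple randomisation.

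None of this removes the mismatch. The protocol chooses four factors important enough to balance on, then fixes a primary test that makes no use of them.

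**Conclusion.** The point holds as a matter of efficiency, not validity. The primary test and those for hospital and ICU mortality ignore the factors used in allocation. For a combined prognostic SD of 0.45 to 0.75 on the logit scale, actual size is about 3.5 to 4%, and about 3 to 4 points of power are forgone, with the apportionment shown above. With weaker factors the total is about 2 points or less; with stronger ones it is 5 or more.

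The direction is secure. The size rests on the Appendix 4 between-ICU variation carrying over to 30-day mortality, on assumed age and diagnosis effects, and on close balance. The change is worth making because it is cheap, not because the present analysis would mislead.

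**What to change.** In section 3.22, make the primary analysis a regression of 30-day mortality on allocation, adjusted for age, sex, broad diagnostic category and recruiting ICU. One suitable form is logistic regression with ICU as a random effect, which copes with units that recruit few patients, standardised to a risk difference and risk ratio with 95% confidence intervals. Keep Fisher's exact test as the supporting unadjusted result. Do the same for hospital and ICU mortality.

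No new data or patients are needed: the factors must already be supplied at the randomisation call for minimisation to run. The cost is more than a change of words. The form of the age term, the diagnostic categories, the standardisation and the handling of small centres must be pre-specified before any unblinded analysis. One stratum per ICU could be sparse: with the planned minimum of 30 units the average is 1692 / 30 ≈ 56 patients each, and some units would have far fewer.

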3.23 Subgroup and exploratory analyses

Additional analyses will explore:

- The effect of early tracheostomy on length of hospital stay, 30 day and hospital mortality in subgroups with different severity of illness determined by APACHE II scoring on ICU admission
- The effect of early tracheostomy on length of hospital stay, 30 day and hospital mortality in broad subgroups (intracranial pathology, respiratory infections etc.) with different causes of respiratory failure
- The effect of early tracheostomy on length of hospital stay, 30 day and hospital mortality in subgroups with different tracheostomy procedures (percutaneous or surgical), assuming sufficient patients in the “late” arm have a tracheostomy to allow this analysis.
- The effect of early tracheostomy on length of hospital stay, 30 day and hospital mortality in subgroups defined by the grade of the primary operator, assuming sufficient patients in the “late” arm have a tracheostomy to allow this analysis.
- The effect of early tracheostomy on length of hospital stay, 30 day and hospital mortality in subgroups of ICUs of varying sizes.
- Whether the duration of ventilatory support can be predicted using a model based on clinical and laboratory information available on days 1-4, and whether the subsequent use of tracheostomy adds explanatory power to the model.

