3.3 The intervention

This trial is not introducing a new procedure but will be evaluating the *timing* of tracheostomy. Specifically:

“Early” tracheostomy:
Tracheostomy to be performed on day 1-4 post admission to ICU

Compared with

“Late” tracheostomy:
No tracheostomy before day 10 post admission to ICU

There is no “usual treatment” arm *per se* as we identified a wide spread of tracheostomy timings in the literature and in the SICSAG audit data. However both of these sources of data suggested that tracheostomies are most commonly placed on day 10-11 following ICU admission. Therefore the timing of tracheostomy placement in the “late” tracheostomy group has been set at day 10 or later to reflect average “usual treatment”.

There will be a number of patients in whom either a tracheostomy will not be required on day 10, either because ventilatory support is no longer needed or the clinicians are reasonably certain that the patient will only need ventilatory support for a further brief period.

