3.11 Clinical management of the 'early' tracheostomy arm

Patients allocated to this arm will have either a percutaneous or surgical tracheostomy at any time during day 1 to day 4 following ICU admission. The technique for tracheostomy will be determined by local practice and will be recorded. Immediate adverse events will be recorded.

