3.12 Clinical management of the 'late' tracheostomy arm

Patients allocated to this arm should not have a tracheostomy before day 10 following ICU admission.

The clinician responsible for their care will review their need for a tracheostomy at day 10, when either of the following strategies may be followed:

- (a) a percutaneous or surgical tracheostomy is performed on or after day 10

or

- (b) no tracheostomy is carried out as it is no longer appropriate to do so (or the patient is no longer in ICU).

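### Subgroups by tracheostomy technique and operator grade are defined by the procedure done after randomisation, so comparing arms within them is biased in a direction that cannot be known in advance

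*Protocol*

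**What the plan says.** Section 3.23 of the protocol lists additional analyses of the effect of early tracheostomy on length of hospital stay, 30-day mortality and hospital mortality. One bullet takes "30 day and hospital mortality in subgroups with different tracheostomy procedures (percutaneous or surgical), assuming sufficient patients in the" late arm receive the procedure. The next repeats this "in subgroups defined by the grade of the primary operator, assuming sufficient patients in the" late arm have one. That proviso shows that membership depends on a tracheostomy actually being performed.

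The two arms reach that point very differently:

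- Early arm (3.11): "Patients allocated to this arm will have either a percutaneous or surgical tracheostomy at any time during day 1 to day 4" after ICU admission. On technique: "The technique for tracheostomy will be determined by local practice and will be recorded".
- Late arm (3.12): "Patients allocated to this arm should not have a tracheostomy before day 10 following ICU admission". At the day 10 review one permitted outcome is that "no tracheostomy is carried out as it is no longer appropriate to do so (or the patient is no longer in ICU").
- Section 3.3 expects some late-arm patients never to have one, "either because ventilatory support is no longer needed or the clinicians are reasonably certain" that only a brief further period of support is needed.

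The mortality clock starts at randomisation (3.4). Minimisation uses age, sex, diagnostic category and ICU (3.9), not technique or operator. Nothing says that technique or operator grade is declared before allocation.

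**The concern.** A subgroup analysis keeps the protection of randomisation only if membership is fixed before allocation, or at least cannot be affected by it. The other subgroups in 3.23 (admission APACHE II, cause of respiratory failure, ICU size) meet that test. These two do not.

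Two selection effects separate the arms:

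1. **Survival to the procedure.** Late-arm patients who die before day 10 have no technique and no operator, so they drop out. Early-arm deaths over the same days stay in.
2. **Continuing need.** Late-arm patients who recover, leave ICU or look close to weaning also drop out. Their early-arm counterparts stay in.

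Hospital stay is affected too. Under the protocol, a late-arm member must still be in ICU around day 10, which puts a floor under their stay. The early arm has no such floor.

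At stake is a published statement that early tracheostomy helps or harms when done by a given technique or grade of operator, when the difference may come only from who was counted. The proviso about sufficient patients concerns precision. More patients would give a tighter estimate of a biased quantity.

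**Working it through.** **Reference figures.** The protocol gives no figure for these subgroups, so its sample size supplies the yardstick. Section 3.20 has 30% late-arm mortality, a 21% relative reduction (0.30 × 0.79 = 23.7%, a 6.3-point difference), alpha 0.05 and 80% power. Taking alpha as two-sided (an assumption), the two-proportion formula gives 776 per arm. The continuity correction, n/4 × [1 + √(1 + 4/(n × 0.063))]², gives 808 per arm, 1616 in total, which matches the protocol. The final size is 846 per arm.

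**Assumptions for the bias.** No true effect; 30% 30-day mortality in both full arms; every early-arm patient has the procedure; no late-arm crossover. The protocol does not give the timing of deaths, the share of the late arm that receives a tracheostomy, or the link between that and severity. These are shown as ranges.

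**Step 1: survival to the procedure.** Let f be the share of 30-day deaths that occur before the late tracheostomy, and d = 0.30f. Mortality among late-arm patients alive at that point is (0.30 − d)/(1 − d), against 30% in the early arm.

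| f | d | late-arm mortality | relative risk, early/late | difference |
|---|---|---|---|---|
| 20% | 0.06 | 0.24/0.94 = 25.5% | 1.18 | 4.5 points |
| 30% | 0.09 | 0.21/0.91 = 23.1% | 1.30 | 6.9 points |
| 40% | 0.12 | 0.18/0.88 = 20.5% | 1.47 | 9.5 points |

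As a cross-check, take a constant hazard and randomisation on day 3, so that day 10 falls 7 days later. Survival to that point is 0.7^(7/30) = 0.920. Late-arm mortality is 1 − 0.7/0.920 = 23.9% and the relative risk is 1.25. The implied f is 0.080/0.30, about 27%, within the range above.

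**Step 2: continuing need.** Let t be the share of late-arm day-10 survivors who receive a tracheostomy, k the ratio of their later mortality to that of survivors who do not, and m the step 1 mortality. Mortality in the late subgroup is then k × m/(t × k + 1 − t).

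- f = 30%, t = 50%: relative risk 1.30, 1.08, 0.98 and 0.87 for k = 1, 1.5, 2 and 3.
- Lowest value, f = 20%, t = 30%, k = 3: 3 × 0.255/1.6 = 47.9%, relative risk 0.63.
- Highest value, f = 40%, k = 1: relative risk 1.47.

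Over f = 20-40%, t = 30-70% and k = 1-3 the spurious relative risk runs from 0.63 to 1.47. The late subgroup holds about 223 (846 × 0.88 × 0.3) to 557 (846 × 0.94 × 0.7) patients, against up to 846 early. Values of k below 1 were not examined and would extend the upper end.

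**Step 3: simulation.** 1692 patients, no true effect, 1000 replicates per scenario, Fisher's exact test. Mortality depended on a latent severity score. All early patients were compared with late patients alive 7 days after randomisation and still needing the procedure (44-46% of the late arm), all taken as one technique.

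| link between severity and need | late-subgroup mortality | false positives, subgroup | false positives, all randomised |
|---|---|---|---|
| none | 23.3% | 68% | 4.6% |
| weak | 26.7% | 21% | 5.6% |
| moderate | 29.4% | 5.4% | 4.4% |
| strong | 31.2% | 8.2% | 5.2% |

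The subgroup test holds its level only where the two effects happen to cancel. The comparison of all randomised patients stays near 5% throughout. With patients split between techniques, each subgroup would be smaller and false positives fewer, but the bias in the estimate would remain.

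**The case against.** The best defence is that these are additional, exploratory and conditional analyses. The principal comparisons in 3.22 are by allocation, and the primary outcome, the secondary mortality outcomes and the sample size do not use these subgroups. That stands, and it limits the severity.

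It could also be said that technique follows local practice, so the technique subgroup might have been meant at unit level. That would be sound, but the proviso about late-arm patients having a tracheostomy ties the wording to the procedure done. Section 3.13 leaves the choice to the responsible consultant, and operator grade has no unit-level form in the text.

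Three stronger readings are tempting and are not supported:

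- **A net bias against early tracheostomy.** Losing early late-arm deaths does work that way, but 3.3 and 3.12 also select patients who still need support, which can offset or reverse it. A relative risk of 1.7 follows if half of deaths come first (0.15/0.85 = 17.6%), but the protocol gives nothing to support that share, and the figure ignores the second effect.
- **The same fault in the last bullet of 3.23.** That bullet asks whether ventilation time can be predicted and whether later tracheostomy adds explanatory power. It compares no arms and claims no treatment effect. Timing needs care in such a model, but that is a separate matter.
- **Complete exclusion of early late-arm events.** Section 3.20 expects about 2% crossover in the late arm, so a few late-arm patients may enter before day 10.

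**Conclusion.** The point holds for the two bullets on technique and operator grade. As worded, they condition on an event after randomisation that falls at different times, and in different kinds of patient, in the two arms. The result cannot be read as an effect of early tracheostomy.

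The survivor component alone is worth a relative risk of about 1.2 to 1.5, or 4.5 to 9.5 points, against a target difference of 6.3 points. With selection on need, the illustrative range is about 0.6 to 1.5 and spans no effect. These sizes rest on the assumed timing of deaths, late-arm uptake and severity link. The structural conclusion does not depend on them. An unknown direction makes the estimate hard to interpret; it does not make it safe.

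This is a moderate correction: it concerns exploratory analyses and leaves the primary intention-to-treat result untouched.

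**What to change.** - **Technique.** Define the subgroup by a factor known before randomisation, such as the ICU's usual technique, with a mixed category because 3.13 admits centres using either or both. Compare all randomised patients by allocation, with a test of interaction. ICU is already a minimisation factor, which helps balance.
- **Operator grade.** Replace it with a site-level usual-practice variable, or drop the comparison between arms. Asking for the intended operator at randomisation would not work well in the late arm: the procedure may be a week or more away or never happen, and 3.24 notes that consultants hand over daily or weekly.
- **Actual technique and operator grade.** Report descriptively within arm only.
- **Proviso on numbers.** Remove it for these bullets, since every randomised patient would then be included.

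The cost is a change to two bullets and one or two site-level items, preferably recorded before each unit starts recruiting. The downside is that usual technique may differ from the one used, which would blur a real difference between techniques.
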